7.3 Handling of Missing, Incomplete and Repeat Data

Missing and incomplete data are usually due to lost to follow-up, revision, death and patient withdrawal. A complete accountability along with the explanation for lost-to-follow-up, death, revision, and withdrawn patients will be provided in the final study report and these subjects will be treated as censored at the date of lost-to-follow up in the survival analysis. The missing due to revision will be treated as device failure. A complete assessment of the informative/non-informative missing data will be performed. In case of missing outcome values at designated time points, the last observation carried forward (LOCF) method will be used.

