2.3 Study duration

It is expected to enroll all patients within 12 months. Each patient will be called for follow-up investigations after 3 months, 1 year, 3 years, 5 years, and 10 years.

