3.4 Complications/adverse events/lost-to follow-up

Complications and adverse events are noted at each follow-up interval. For completed observations due to death of the patient, explantation of the device or patient's address unknown the latest status will be recorded as an endpoint. Patients will be considered lost to follow-up after they have missed two visits and all attempts to locate and evaluate them have failed. Patients who refuse to attend follow-up or patients unable to attend follow-up will be assessed by telephone if possible. Minimal data concerning the implant status should be acquired by telephone.

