7.4 Derived Data

The following variables will be derived from the collected data:

- ❖ **Age:** The age will be calculated as the exact number of days between the date of birth and date of entry into study converted to years (i.e. difference in days/365.25).
- ❖ **Body Mass Index (BMI):** BMI is obtained by dividing the weight (kg) at enrollment by the square of height (m) i.e. weight (kg)/ height² (m).

CONFIDENTIAL AND PROPRIETARY

This document contains information that is confidential and proprietary to Smith & Nephew PLC and Smith & Nephew, Inc. and is intended for use only by Smith+Nephew and its manufacturer. It shall not be reproduced or copied in whole or in part, nor shall the contents be disclosed by any means without prior written permission from Smith+Nephew, nor shall anyone make any use of it that is contrary to the expressed or implied wishes of Smith+Nephew.

Statistical Analysis Plan

Multicenter Clinical Observation Using the Cementless Version of the
POLARSTEM™

Number: D10070
ST: 1133
Version: 1.0, 30-Nov-2021
Page: 10 of 19

- ❖ **Baseline:** Preoperative examination visit is considered as the baseline visit for all parameters for which data is collected at that time point.
- ❖ **Safety population indicator variable:** A binary variable will be defined if the patient receives study treatment then the patient is included in the safety population or not. Only patients indicated as included in the safety population will be used in the safety population analysis.
- ❖ **FAS set indicator variable:** A categorical variable will be defined to indicate if the patient receives study treatment and attends at least one post-baseline assessment then the patient is included in the full analysis set. Only the patients in the included category will be included in the full analysis set.
- ❖ **Per-protocol set indicator variable:** A categorical variable will be defined to indicate if the patient is in the full analysis set and have no significant protocol deviations and meet the inclusion/exclusion criteria. Only the patients in the included category will be included in the per-protocol analysis set.
- ❖ **Visit Interval:** days between baseline assessment and Study Visit defined as: Date of Study Visit – date of baseline assessment.
- ❖ **Survival time (days):** End of study/Death/Loss to Follow-up/revision date – baseline assessment date+1; In months, divide days by 30.4375; In years, divide days by 365.25.

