- ❖ **Withdrawn Subject:** A withdrawn subject will be considered as one who does not complete the study because of to loss to follow-up or the early termination or any other known reason.
- ❖ **Completed Subject:** This study has been terminated early, a subject will be considered as having completed the study if he/she completed the 10 year visit for the study prior to its termination.

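### SAP 7.3 and 7.4 end survival time for unrevised hips at the loss or end-of-study date, not at the last date stem status was known; taken literally, this slightly overstates 10-year stem survival

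*SAP*

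**What the plan says.** Stem survival at 3 months and 1, 3, 5 and 10 years is the primary endpoint (SAP 5.1), estimated by Kaplan-Meier with 95% intervals (SAP 7.10). The event is stem revision for any reason (Protocol 1.3).

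On when follow-up ends:

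- SAP 7.3, on lost, deceased and withdrawn patients: "these subjects will be treated as censored at the date of lost-to-follow up in the survival analysis". Revision counts as device failure.
- SAP 7.4 ends survival time at "End of study/Death/Loss to Follow-up/revision date", without an order of precedence.
- SAP 7.4 on withdrawal: "A withdrawn subject will be considered as one who does not complete the study because of to loss to follow-up or the early termination" or for any other known reason. On completion: "This study has been terminated early, a subject will be considered as having completed the study if he/she completed the 10 year visit".
- Protocol 3.4 has the only definition of loss: "Patients will be considered lost to follow-up after they have missed two visits and all attempts to locate and evaluate them have failed". For observations ended by death, explantation or an unknown address, "the latest status will be recorded as an endpoint". For patients who refuse or cannot attend, "Minimal data concerning the implant status should be acquired by telephone".
- Protocol 2.3 sets visits "after 3 months, 1 year, 3 years, 5 years, and 10 years".

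No section says that an unrevised hip is censored at the last visit or contact at which the stem was known to be in place.

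**The concern.** Kaplan-Meier divides the revisions seen by the hips counted as at risk. A hip kept in the risk set after contact has ended adds to the denominator but usually cannot add to the numerator. The estimated hazard is then too low and survival too high. The number at risk and the confidence interval also suggest more follow-up than there was.

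The visits are far apart, so the choice of date matters. The definition of loss also leaves two groups without a date. A patient last seen at 5 years has only the 10-year visit left and cannot miss two. Patients who withdraw or are stopped by early termination are sent by SAP 7.3 to a loss date that they need not have. Two programmers following this text could produce different primary results.

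**Working it through.** **Dating.** If loss is dated at the second missed visit:

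| Last seen | Second missed visit | Unobserved time counted as event-free |
|---|---|---|
| 3 months | 3 years | 2.75 years |
| 1 year | 5 years | 4 years |
| 3 years | 10 years | 7 years |
| 5 years | none | undefined (5 years if carried to year 10) |

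**Inputs.** From the documents: 30% drop-out over 10 years (Protocol 2.2), the visit times (Protocol 2.3) and 225 enrolled (SAP 7.15). Assumed, because the documents give no revision rate: 5% true 10-year revision (range 2% to 10%), constant hazards, drop-out unrelated to revision, and nothing learned after the last visit. The plan has no figure of its own on this point to reproduce.

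**Formula.** The revision hazard is −ln(0.95)/10 = 0.005129 per year. The share still in follow-up at year t is 0.70^(t/10): 0.9911, 0.9650, 0.8985, 0.8367 and 0.7000 at the five visits. The differences give the shares last seen at surgery, 3 months, 1, 3 and 5 years: 0.9%, 2.6%, 6.6%, 6.2% and 13.7%. In each interval let O be the share truly observed and U the share no longer seen but not yet censored. The reported hazard is then close to 0.005129 × O/(O+U).

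**Second missed visit, with patients last seen at 5 years carried to year 10:**

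| Years | O | U | O/(O+U) | × length |
|---|---|---|---|---|
| 0–0.25 | 0.9911 | 0.0089 | 0.9911 | 0.248 |
| 0.25–1 | 0.9650 | 0.0350 | 0.9650 | 0.724 |
| 1–3 | 0.8985 | 0.0926 | 0.9066 | 1.813 |
| 3–5 | 0.8367 | 0.1283 | 0.8670 | 1.734 |
| 5–10 | 0.7000 | 0.1985 | 0.7791 | 3.895 |

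The last column sums to 8.414. Reported revision = 1 − exp(−0.005129 × 8.414) = 4.22%, so survival is overstated by 0.78 points.

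**Other datings, same formula:**

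- Last-known-status date: U = 0, sum 10, reported 5.00%, no error.
- Second missed visit, patients last seen at 5 years censored there: the last row becomes 5 × 0.7000/0.7619 = 4.594, the sum 9.113, and the result 4.57% (4.56% by exact integration). Overstatement about 0.44.
- Every lost patient carried to a 10-year end of study: O+U = 1 throughout, sum 7.942, reported 3.99%. Overstatement about 1.0.
- Front-loaded revision (cumulative hazard proportional to √t), dated as in the table: interval weights 0.158, 0.158, 0.232, 0.159 and 0.293 give a weighted sum of 0.886. Then 1 − exp(−0.05129 × 0.886) = 4.44%. Overstatement about 0.56.

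**Sensitivity of the 0.78 figure.** It becomes 0.32 at 2% true revision and 1.55 at 10%. It becomes 0.38 at 15% drop-out and 1.23 at 45%. If all losses follow the 3-year visit it is 1.04. If status is known for half of the drop-outs it falls to 0.42.

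**Precision.** In 5,000 simulated trials of 225 implants, with the dating in the table against last-known status, 193 against 150 hips are counted at risk at 10 years. The mean SE is 1.36 against 1.62 points and the mean 95% interval width 5.7 against 6.8 points. Coverage stays near 95% either way.

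**Where the last-known-status rule errs.** If revisions up to drop-out are learned but revision-free status is not, that rule reports 5.30%. The second-missed-visit date then reports 4.47% (last seen at 5 years carried to year 10) or 4.84% (censored at 5 years). In the latter case the last-known-status rule has the larger error, 0.30 against 0.16.

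**Drop-out related to revision, overall rate held at 5%.** With a 1.5-fold revision hazard in drop-outs, the loss-date run (carried to year 10) and the last-status run give 3.89% and 4.59%, both too low. With a halved hazard, and patients last seen at 5 years censored there, they give about 5.1% and 5.6%, both too high.

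**The case against.** The strongest reply is that the usual reading of a loss date in a survival analysis is the date on which follow-up ended. Protocol 3.4 leans that way: for a patient whose address is unknown the latest status is recorded, and implant status is sought by telephone. The two-missed-visits sentence decides who counts as lost; it does not say when. SAP 7.3 promises full accountability and an assessment of informative missingness, and SAP 7.6 tabulates patients expected and present at each visit, so thin late follow-up would be visible. The CRF, which might settle what date is recorded, is not among the documents.

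Much of this stands. A reader might infer that the reported survival will be inflated, but the documents do not show that: if the recorded loss date is already the last-status date, there is no error. What does not stand is the idea that the documents set that date. Recording the latest status fixes what is known, not where survival time ends, and the SAP does not refer to it. Telephone contact helps only for patients who are reached. The accountability and attendance tables describe loss without dating it. The SAP names loss and end of study as its dates, and the only definition of loss falls years after the last contact.

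**Conclusion.** The concern holds as a conditional one. The censoring date for the primary endpoint is not tied to last known stem status, and literal use of the stated dates favours the device. Under the assumptions listed, the overstatement at 10 years is about 0.4 to 0.8 points with the two-missed-visits date, about 1.0 point if all lost patients are carried to a 10-year end of study, about 0.6 with front-loaded revision, and zero if last-status dates are what sites record. None of these is a strict ceiling, since the size moves with the revision rate, the amount of drop-out and its timing. The effect of the early-termination date itself was not modelled.

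The error is below one sampling SD (1.4 to 1.7 points) and the analysis is descriptive, so no pass/fail conclusion turns on it. Nor should a reader infer that running both datings bounds the truth. The calculations in which they do so assume that drop-out is unrelated to revision; without that assumption both runs can fall on the same side. The change is worth making because it concerns the primary endpoint and costs little.

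**What to change.** In SAP 7.3 and 7.4, censor every unrevised hip at the last date stem status was known: a visit, a documented telephone contact, or death with the stem in place. Apply this alike to loss, withdrawal, early termination and end of study. Report numbers at risk at each of the five time points. State in the report how any revision after the last contact was learned. Add one Kaplan-Meier run using the declared-loss or end-of-study date, labelled as a sensitivity analysis and not as a bound.

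The cost is SAP wording, one derived date and one extra run. Visit dates are already needed for the visit interval in SAP 7.4 and attendance for SAP 7.6. Whether telephone contact dates are captured cannot be seen without the CRF. The downside is a slightly lower survival estimate with a wider interval, and some overstatement of failure (about 0.3 points at 5%) if revisions are learned after the last contact but revision-free status is not.

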3.3 Follow-up

The follow-up schedule is shown in table 1.

Table 1: Time windows for investigations

	Time-window	HHS/HOOS	Clinical	Radiographic
Preoperative	45–0 days	X	X	-
3 months	10–14 weeks	X	X	X
1 year	11–13 months	X	X	X
3 years	36–38 months	X	X	X
5 years	60–63 months	X	X	X
10 years	120–123 months	X	X	X

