3 STUDY DESIGN

The study is a prospective long-term multicenter clinical observation study. Overall a minimum of 225 patients were enrolled consecutively into the study at 3 sites. Patients enrolled into the study had at least one of the following indications:

- Primary or Secondary coxarthrosis
- Rheumatoid arthritis
- Developmental dysplasia of the hip
- Fracture or avascular necrosis of the femoral head

The patients were enrolled consecutively over 12 months and followed up for 10 years with observations at 3 months, 1 year, 3 years, 5 years and 10 years.

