7 STATISTICAL ANALYSIS

7.1 General

Smith & Nephew's Global Biostatistics group will conduct the statistical analysis for this study. Unless otherwise stated, all significance tests and hypothesis testing will be two-sided, performed at the 5% significance level. Resulting p-values will be quoted and 95% two-sided confidence intervals will be generated where appropriate. All p-values will be rounded to three decimal places, p-values less than 0.001 will be presented as '<0.001' in all tables.

Baseline data, outcome variables and adverse events will be summarized according to the nature of the variable. Categorical and ordinal variables will be summarized with frequencies and percentages. Continuous variables will be summarized with the following summary statistics: number of observations, mean, median, standard deviation, minimum and maximum values. The outcome variables will be summarized for all recorded time points.

Appropriate parametric and/or non-parametric analyses will be chosen for statistical analysis. The analysis of continuous variables will be done using a paired-sample t-test if appropriate, to test for differences between the baseline and end of study outcomes. The Wilcoxon rank-sum tests will be explored if the data is non-normal.

If data allows, Kaplan-Meier estimates will be calculated for the survival data otherwise only the survival proportion with a 95% confidence interval will be reported..

All analyses will be performed in SAS version 9.4 (or later).

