7.2 Analysis Populations

All subjects who provide informed consent are considered study participants. Study populations are defined as follows:

CONFIDENTIAL AND PROPRIETARY

This document contains information that is confidential and proprietary to Smith & Nephew PLC and Smith & Nephew, Inc. and is intended for use only by Smith+Nephew and its manufacturer. It shall not be reproduced or copied in whole or in part, nor shall the contents be disclosed by any means without prior written permission from Smith+Nephew, nor shall anyone make any use of it that is contrary to the expressed or implied wishes of Smith+Nephew.

Statistical Analysis Plan

Multicenter Clinical Observation Using the Cementless Version of the POLARSTEM™

Number: D10070
ST: 1133
Version: 1.0, 30-Nov-2021
Page: 9 of 19

- **Full analysis population (FAS)**, including all subjects that were included in the study, who received study treatment and attended at least one post baseline assessment.
- **Per protocol analysis population**, including all subjects in the full analysis population, have no significant protocol deviations and meet the inclusion/exclusion criteria.
- **Safety population**, including all subjects who have received study treatment.

Statistical analysis will be performed using each of the subject populations as follows: Analysis of primary, secondary and exploratory variables will be performed separately using both the FAS and the Per-Protocol Set. All safety analyses will utilise the Safety Population. Demographic characteristics will be summarized for each analysis population. Demographic characteristics will be summarized on a subject level. For bilateral subjects the data corresponding to the date of the hip's first enrolment into the study will be used.

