7.11 Analysis of Secondary Endpoints

- Harris Hip Score (HHS)

CONFIDENTIAL AND PROPRIETARY

This document contains information that is confidential and proprietary to Smith & Nephew PLC and Smith & Nephew, Inc. and is intended for use only by Smith+Nephew and its manufacturer. It shall not be reproduced or copied in whole or in part, nor shall the contents be disclosed by any means without prior written permission from Smith+Nephew, nor shall anyone make any use of it that is contrary to the expressed or implied wishes of Smith+Nephew.

Statistical Analysis Plan

Multicenter Clinical Observation Using the Cementless Version of the POLARSTEM™

Number: D10070
ST: 1133
Version: 1.0, 30-Nov-2021
Page: 17 of 19

- HOOS Score (Hip Dysfunction and Osteoarthritis Outcome Score), which includes the complete WOMAC Osteoarthritis Index
 - The different dimensions of and the overall HHS, and WOMAC from HOOS scores at all recorded time points and end of study will be summarized using mean, median, SD, minimum, and maximum. A paired sample t-test (or a non-parametric equivalent such as the Wilcoxon signed-rank test) will be used to test the difference between preoperative and postoperative scores.
- Radiological: At all recorded time points (from the perioperative through the 10 year postoperative follow-up), the following analyses would be carried out:
 - For general findings: At the acetabulum position, cranial migration (mm), medial migration (mm) and tilted angle would be summarized using descriptive characteristics for continuous variables; At the stem position, varus tilting, valgus tilting and sunken (mm) will be summarized using descriptive statistics for continuous variables; Integration in general/acetabulum, integration in general/stem and ectopic ossification will be summarized using descriptive statistics for categorical variables.
 - Within the cup and the stem (by zone): The number and percent of hips with osteolysis will be summarized; for seams (0mm, 1mm, 2mm &>2mm), atrophy (none, mild, moderate & severe) and hypertrophy (none, mild, moderate & severe) their frequencies (n) and percentages will be presented.

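### SAP 7.3 makes LOCF the only method for missing outcome values, with no maximum gap and no exempt outcome, so a filled 10-year score or film value could be nominally 5 to 9.75 years old.

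*SAP*

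**What the plan says.** SAP 7.3 states: "In case of missing outcome values at designated time points, the last observation carried forward (LOCF) method will be used". No other method for missing outcome values appears in either document. The same section has separate rules for survival (censoring) and for data missing because of revision (counted as a failure of the device). It also promises an assessment of whether missingness is informative, but gives no method and no consequence for LOCF.

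Protocol 2.3 sets the schedule: "Each patient will be called for follow-up investigations after 3 months, 1 year, 3 years, 5 years, and 10 years". SAP 3 agrees: "followed up for 10 years with observations at 3 months, 1 year, 3 years, 5 years and 10 years". The full analysis set in SAP 7.2 takes subjects "who received study treatment and attended at least one post baseline assessment", so someone seen only at 3 months is included.

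On reporting, SAP 7.1 says "The outcome variables will be summarized for all recorded time points" and plans a paired t-test "to test for differences between the baseline and end of study outcomes". SAP 7.11 says HHS and WOMAC "at all recorded time points and end of study will be summarized using mean, median, SD, minimum, and maximum", with a paired test against the preoperative score. Radiographic findings are summarised at recorded time points only, with no end-of-study summary and no test.

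**The concern.** The longest gap in the schedule, from 5 to 10 years, comes just before the visit that carries the long-term claim. A patient who misses the 10-year visit has no value less than about 5 years old to carry forward. As written, LOCF would present that old value as a 10-year result.

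Three features add to this:

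- Nothing bars carrying a preoperative score. Protocol 3.1 lets patients take the HOOS home and return it later, so a patient can attend a visit, enter the full analysis set and still have no postoperative HOOS.
- Nothing bars carrying a value past death. For revision, calling it a device failure assigns no score and no film finding.
- The definition of a completed subject in SAP 7.4 says the study was terminated early. That may add missing 10-year values; no count is given.

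Radiographic findings, HHS and HOOS are the main parameters in the Protocol Summary and appear under the primary objectives in SAP 4.1, although SAP 5.2 lists them as secondary endpoints. With one arm, there is no comparator in which the same distortion might cancel.

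**Working it through.** The plan states no figure for the age of a carried value, so there is none to reproduce.

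**1. Age of a filled 10-year value.** Age = 10 minus the nominal time of the last attended visit (Protocol 2.3).

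- Last seen at 5 years: 10 − 5 = 5 years
- Last seen at 3 years: 10 − 3 = 7 years
- Last seen at 1 year: 10 − 1 = 9 years
- Last seen at 3 months: 10 − 0.25 = 9.75 years

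With the windows in Protocol 3.3 ("Table 1: Time windows for investigations"), the lower end is (120 − 63)/12 = 4.75 years and the upper end is 123/12 − 70/365.25 = 10.06 years. A carried preoperative score would be at least 10 years old.

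**2. How many values.** Protocol 2.2 plans for 30% drop-out over 10 years, and SAP 7.15 reports 225 subjects. 0.30 × 225 = 67.5, so about 68 could lack a 10-year value and about 158 would have one. The 30% is a planning rate for implants, not a measured rate of missing films or scores.

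**3. Films, findings that never regress (scenario).** Assumed: true 10-year frequency 20%; fraction missing d = 0.30; drop-out unrelated to outcome; last visits split equally over 3 months and 1, 3 and 5 years; frequency rising linearly to a plateau at year T, p(t) = 20% × min(t/T, 1). LOCF reports (1 − d) × 20% + d × m, where m is the mean of p(0.25), p(1), p(3) and p(5).

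| T (years) | m | LOCF reports | Relative loss |
|---|---|---|---|
| 1 | 16.25% | 14 + 4.875 = 18.9% | 5.6% |
| 3 | 12.08% | 14 + 3.625 = 17.6% | 11.9% |
| 5 | 9.25% | 14 + 2.775 = 16.8% | 16.1% |
| 10 | 4.625% | 14 + 1.388 = 15.4% | 23.1% |

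Under these assumptions the limits are no loss (plateau before every last film) and 30% (all onset after year 5). The T = 1 to T = 10 range is about 4 to 15% at d = 0.20 and 8 to 31% at d = 0.40.

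**4. Films, regressing findings (scenario).** If a frequency falls from 20% to 10% after the last film, LOCF reports 0.7 × 10 + 0.3 × 20 = 13%, a 30% relative overstatement.

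**5. Scores (scenario).** If every patient declines by δ after the last visit that drop-outs attended, LOCF is too favourable by 0.3δ: 0.03, 0.075 or 0.15 SD for δ = 0.1, 0.25 or 0.5 SD. An observed-case mean is not biased. If only drop-outs decline, both are off by 0.3δ, so that case does not count against LOCF. In the other direction, 0.30/4 = 7.5% of subjects are last seen at 3 months under the equal split. If their score then is 1 SD below the later plateau, LOCF is 0.075 SD too unfavourable, which cancels the δ = 0.25 case exactly.

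**6. Precision.** Treating copied values as observed shrinks an interval by √(1 − d) at equal SD: √0.70 = 0.84 of the observed-case width (0.89 at d = 0.20, 0.77 at d = 0.40).

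**The case against.** The strongest reply is that the by-visit tables may not contain filled values at all. SAP 7.1 and 7.11 speak of recorded time points, which can mean observed data only. That reading is most plausible for films, which have no end-of-study summary and no test; on it, the film figures in step 3 do not arise. This stands as a possible reading, but the SAP does not state it, and it sits badly with SAP 7.3, which applies LOCF at designated time points. For scores it is not a full answer, because LOCF could still supply the end-of-study value. The table shells named in SAP 2, which might settle the matter, are not among the documents.

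Second, a reader might infer that LOCF makes the stem look better than it is. The documents do not support a sign. SAP 7.11 includes graded findings, and nothing says they can only worsen. Three-month scores may precede full recovery, and a carried preoperative score sets the change to zero, which counts against the device where patients have improved. This part of the reply stands.

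Third, some protection exists. SAP 7.3 promises the missingness assessment, and comparing the number of observations (SAP 7.1) with the present-at-visit counts (SAP 7.6) would show roughly how many values were filled. Neither limits LOCF, and neither shows which values were filled or how old they are.

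Fourth, the SAP's primary endpoint is survival, and no success criterion or margin rests on the filled values. That is correct and limits the consequence.

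**Conclusion.** The concern holds as a defect in a stated rule. SAP 7.3 permits a 10-year HHS, WOMAC or radiographic value that is nominally 5 to 9.75 years old. It also does not rule out carrying a preoperative score or carrying a value past death. The age range follows from the visit schedule and the analysis-set definition alone.

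The size and direction of bias cannot be fixed from the documents. The 6 to 23% relative loss in film frequency is an illustration that needs 30% missing, a true frequency of 20%, equally split last visits and findings that never regress; steps 4 and 5 show effects of similar size the other way. The overstated precision does not depend on the sign: wherever LOCF is applied, copied values count as 10-year observations.

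Two stronger conclusions should not be drawn: that the 10-year tables will certainly hold filled values, since an observed-only reading is open, and that the survival result is compromised. Kaplan-Meier estimation in SAP 7.10 uses censoring and is unaffected. The change should be made, but it concerns secondary endpoints.

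**What to change.** In SAP 7.3 replace the LOCF sentence with:

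> Radiographic outcomes are reported on observed films, with the number of hips filmed at each visit. HHS and WOMAC change from baseline is estimated from observed values with a likelihood-based repeated-measures model (visit as factor, hips clustered within subject). No value is carried past revision or death; these are counted separately at each visit. LOCF is at most a sensitivity analysis.

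This needs SAP wording and modest programming, with no new data. The displayed 10-year n falls to about 158 of at most 225 subjects if 30% are missing (films are counted by hip). Against LOCF at equal SD, an observed-case score interval is 1/0.837 = 1.195 times as wide, about 20% wider. With the model the factor is √(1 + (0.3/0.7)(1 − r²)), where r is the correlation between the last observed and the 10-year score. Assuming r = 0.5 or 0.7 gives 1.150 or 1.104, so about 15% or 10% wider. The model does not remove bias if drop-outs fare worse in ways their observed scores do not predict; observed-case means and LOCF share that limit.

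Separately, SAP 7.1 names the Wilcoxon rank-sum test as the non-parametric option for baseline versus end of study. That comparison is paired, and SAP 7.11 already names the signed-rank test. Change rank-sum to signed-rank in 7.1.
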